6 STUDY SETTING

Participants will primarily be recruited from St Stephen's Centre at Chelsea and Westminster Hospital and affiliated HIV and pain clinics in London. St. Stephen's Centre is one of the largest HIV centres in Europe. Recruiting participants from Chelsea and Westminster Hospital NHS Trust will ensure participants recruited into the study are representative of the population of interest.

7 SAMPLE AND RECRUITMENT

7.1 Eligibility Criteria

7.1.1 Inclusion criteria

- Adults aged 18 years or older.
- Living with HIV.
- A positive screen for peripheral sensory neuropathy, as indicated by: presence of self-reported bilateral foot pain and/or numbness in a symmetrical distribution (43).
- Positive screen for symptoms of neuropathic pain in the feet, as indicated by a score of >3 on the patient reported outcomes section of the Neuropathic Pain Interview, which has

previously been shown to have greater than 80% sensitivity and specificity for identifying people with neuropathic pain conditions (48, 49)

- Pain in the feet present most days for at least 3 months.
- Average pain intensity of ≥ 4 on a scale from 0 (no pain) to 10 (pain as bad as you can imagine)(50).
- Average interference of pain with daily activities is ≥ 4 on scale ranging from 0 (no interference) to 10 (unable to carry on any activities) (51).

7.1.2 Exclusion criteria

- Presence of excessive alcohol consumption, hypothyroidism, vitamin B12 deficiency, diabetes, exposure to isoniazid or chemotherapy drug treatment, or a known history of a neuropathy due to a cause other than HIV or antiretroviral treatment (12, 52)
- Unable to conduct interview in English.
- Current diagnosis of dementia or learning disability.
- Unwilling to provide written informed consent.

7.2 Sampling

7.2.1 Size of sample

Approximately 30 participants will be recruited, with roughly equal representation of men, women, ethnic minorities, and people who use recreational drugs. Recruitment will terminate once saturation of themes has been achieved. Thus, while an approximate sample size has been estimated on the basis of convention in qualitative methods and the range of demographic characteristics being sought (53, 54), an exact sample size cannot be determined a priori.

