Planned Study Period	November 2016 to August 2017
Research Question/Aim(s)	To investigate the needs of people with HIV and painful sensory neuropathy for a psychological treatment to reduce the impact of pain on quality of life. To explore the acceptability of an internet-delivered psychological intervention and to tailor the content and delivery format of the intervention to the identified needs of this group.

FUNDING AND SUPPORT IN KIND

FUNDER(S)	FINANCIAL AND NON FINANCIAL SUPPORT GIVEN
(Names and contact details of ALL organisations providing funding and/or support in kind for this study)	
National Institute for Health Research	Financial (salary costs of the CI, and training and research costs)

ROLE OF STUDY SPONSOR AND FUNDER

The lead sponsor, King's College London, will take primary responsibility for ensuring that the design of the study meets appropriate standards and that arrangements are in place to ensure appropriate conduct and reporting. King's College London also provides cover under its No Fault Compensation Insurance, which provides for payment of damages or compensation in respect of any claim made by a research subject for bodily injury arising out of participation in a clinical trial or healthy volunteer study (with certain restrictions).

The funder reviewed and approved the study in the process of the Chief Investigator's fellowship application. The Chief investigator must notify the funder of any publication at the time of submission or at least 28 days prior to publication.

ROLES AND RESPONSIBILITIES OF STUDY MANAGEMENT COMMITTEES/GROUPS & INDIVIDUALS

The study steering group will consist of [name], [name], [name], [name], and two patient representatives, [name] and [name]. The steering group will ensure that the study adheres to the protocol, and meets recruitment, data analysis, and dissemination objectives. [name] will oversee the day-to-day management of the study.

Protocol contributors

[name] drafted the protocol in collaboration with Professors [name] and [name], and [name]. Two patient representatives ([name] and [name]) provided input on the recruitment strategy, questionnaires and interview schedule, and participant information sheet and consent form. Another HIV patient organization (UKCAB) provided feedback on patient-facing study documents.

KEY WORDS:

HIV, pain, peripheral neuropathy, psychological treatment, qualitative research

LIST of CONTENTS

GENERAL INFORMATION	Page No.

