TITLE PAGE	1
RESEARCH REFERENCE NUMBERS	2
SIGNATURE PAGE	3
KEY STUDY CONTACTS	4
STUDY SUMMARY	5
FUNDING	6
ROLE OF SPONSOR AND FUNDER	7
ROLES & RESPONSIBILITIES OF STUDY STEERING GROUPS AND INDIVIDUALS	8
LIST of CONTENTS	9
STUDY FLOW CHART	10
SECTION	
1. BACKGROUND	11-12
2. RATIONALE	11-12
3. THEORETICAL FRAMEWORK	12
4. RESEARCH QUESTION/AIM(S)	12
5. STUDY DESIGN/METHODS	13-14
6. STUDY SETTING	15
7. SAMPLE AND RECRUITMENT	15-17
8. ETHICAL AND REGULATORY COMPLIANCE	17-20
9. DISSEMINATION POLICY	20
10. REFERENCES	21-23
11. APPENDICES	N/A

STUDY FLOW CHART

Table 1. Timeline of Study Activities

Month	Nov '16	Dec '16	Jan '17	Feb '17	Mar '17	Apr '17	May '17	Jun '17	July '17	Aug '17	Sept '17
Recruitment/ screening	X	X	X	X	X	X	X	X	X		
Informed consent, questionnaire and interview completion	X	X	X	X	X	X	X	X	X		
Transcribing	X	X	X	X	X	X	X	X	X	X	
Data Analysis	X	X	X	X	X	X	X	X	X	X	
Dissemination									X	X	X

STUDY PROTOCOL

OPEN Study: Pain management treatment needs interview

1 and 2: BACKGROUND and RATIONALE

The human immunodeficiency virus (HIV) remains a significant global health concern. An estimated 35 million people are infected with HIV worldwide (1, 2); approximately 110,000 infected individuals are in the United Kingdom (3). Antiretroviral therapies have significantly improved survival rates. At the same time, approximately 6,000 individuals are newly infected with HIV in the UK each year (3). Consequently, the prevalence of infected individuals is growing.

In well-resourced countries, the shift in HIV from a terminal illness to a chronic condition has contributed to a greater focus on disease and symptom management (4). Pain in the feet is one of the most predominant symptoms associated with HIV infection and treatment. Approximately 40 to 60% of people with HIV have peripheral sensory neuropathy (HIV-SN); 50-90% of these experience neuropathic pain (5-7).

Painful HIV-SN is associated with increased disability in daily activities, unemployment, and reduced quality of life (8). Additionally, painful HIV-SN is associated with numerous comorbidities, including depression, panic disorder, post-traumatic stress disorder, and substance abuse (9-13). Thus, untreated painful HIV-SN may contribute to significant individual, societal, and economic burden.

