Despite advancements in research on CBT and ACT for musculoskeletal pain conditions, comparable research does not exist for individuals with painful HIV-SN. One systematic review of CBT for neuropathic pain identified only 3 RCTs (26). Only one of these RCTs focussed on HIV-related pain; this study had an unacceptably high dropout rate of 57% (27). Two additional observational cohort studies of group-based CBT for HIV-related pain showed similarly poor adherence (28, 29). There is a clear need for improving psychological interventions for individuals with HIV-related pain. Patient representatives and clinicians practicing in the area of HIV and pain management have been consulted with respect to this issue and have identified the need for better development and implementation of psychological treatments for pain in this population.

Improving psychological treatments for painful HIV-SN will likely require greater consideration of the psychosocial complexities associated with this condition. For example, HIV is most common among gay men, women, ethnic minorities, and intravenous drug users (3, 30). There is recognition of important healthcare disparities and under treatment of pain in these groups (31-33). However, the unique perspectives and needs of individuals in these groups are not typically incorporated into psychologically-based pain management interventions such as CBT/ACT. Moreover, findings from the available qualitative literature suggest that social stigma and interpersonal distrust may influence treatment engagement among individuals with HIV (34-38). However, research is needed to understand how these psychosocial issues can best be addressed within CBT/ACT for pain.

This study will use in-depth interviews to examine the needs of people with painful HIV-SN for a psychologically-based pain management treatment that may be delivered over the Internet. Interview questions will examine the impact of pain on people's lives and how they cope with pain, and participants' treatment needs in terms of treatment content and delivery format. Men, women, ethnic minorities, and people who use recreational drugs will be purposively sampled to ensure that interview responses reflect the views of people most commonly suffering from this condition.

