7.2.2 Sampling technique

Men and women, ethnic minorities, and people who use recreational drugs will be purposively sampled through HIV and pain clinics and community organizations and through chain referral sampling. Purposive sampling across participants with the range of demographic backgrounds identified will ensure that the interview responses are reflective of people with painful HIV-SN who might ultimately be referred to and receive the psychologically-based pain management treatment being developed.

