8.4 Patient & Public Involvement

[name] and [name] are patient representatives located at St. Stephen's Centre at Chelsea and Westminster Hospital and at King's College Hospital, respectively. [name] were consulted about the study during the application for funding of a fellowship to undertake a larger project to develop and test the feasibility of an online psychologically-based pain management treatment for people with painful HIV-SN. Both [name] were enthusiastic about the potential benefits of the new treatment, but identified patient engagement as an important issue. This input solidified the need to incorporate a qualitative study of barriers to patient engagement for the proposed online treatment, which will feed into further treatment development.

The patient representatives were involved in the design of the research in several ways. [name] suggested that a multi-pronged recruitment strategy was the most appropriate to ensure we capture the views of the diversity of people with painful HIV-SN. This informed our recruitment strategy. [name] did not feel that peer/patient interviewers for the qualitative study were appropriate, and, therefore, it was decided that a researcher ([name]) would conduct the interviews. [name] also suggested suitable remuneration (e.g., vouchers) for participants in the interview study. [name] reviewed study documents (e.g., recruitment adverts, information sheet, consent form, questionnaires, and interview schedule) and made several suggestions for re-wording, which were incorporated into the current version of the documents. UKCAB, which is an advocacy group of people living with HIV, also provided feedback on the study documents, which was also incorporated.

[name] will be consulted to provide input on the themes coded from the transcribed interviews to ensure their relevance and appropriateness. [name] will also review a study report that will be given to patients following completion for the study to ensure its comprehensibility and sensitivity.

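### Does the sample mix in Section 7.2.1 need a counting rule for overlapping groups and an explicit link to the saturation stop?

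*Combined protocol and SAP*

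**What the plan says.** Section 7.2.1 gives size and mix in one sentence: "Approximately 30 participants will be recruited, with roughly equal representation of men, women, ethnic minorities, and people who use recreational drugs". The next sentence gives the stop: "Recruitment will terminate once saturation of themes has been achieved". The section adds that the figure of 30 rests on convention in qualitative work and on the spread of backgrounds wanted, and that no exact number can be fixed in advance.

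Section 7.2.2 (Sampling technique) repeats the groups: "Men and women, ethnic minorities, and people who use recreational drugs will be purposively sampled". It gives the purpose: "Purposive sampling across participants with the range of demographic backgrounds identified will ensure that the interview responses are reflective of people with painful HIV-SN". The Background and Rationale says much the same, that these groups "will be purposively sampled to ensure that interview responses reflect the views of people most commonly suffering from this condition".

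Two other places bear on the mix. Section 8.4 records a patient representative's advice that a "multi-pronged recruitment strategy was the most appropriate to ensure we capture the views of the diversity of people with painful HIV-SN". The section on roles and responsibilities states: "The steering group will ensure that the study adheres to the protocol, and meets recruitment, data analysis, and dissemination objectives". None of these gives a number per group, a rule for people who belong to more than one group, or a statement that the mix must be reached before saturation is declared.

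**The concern.** The four groups are not alternatives. Men and women together make up nearly the whole sample, and every participant from an ethnic minority or who uses recreational drugs also has a gender. The intended number from an ethnic minority, or who use recreational drugs, therefore depends on how people are counted, and the two obvious ways differ by a factor of two. The words for approximation in Section 7.2.1 do not stretch that far.

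The stop adds to the unease. Recruitment ends at saturation, and the text does not say whether that is judged across all interviews or within each group. Recruitment could end with one group thinly represented, yet the protocol rests its claim to reflect the affected population on the sampling. The interviews will shape an online treatment for a later feasibility trial, so a need particular to an under-sampled group might not reach the design. A steering group asked to confirm that recruitment objectives were met might also not know which target applies.

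**Working it through.** **Inputs.** N = 30, the four groups and the saturation stop come from Section 7.2.1. The plan gives no figure per group and no sample-size formula, so there is nothing to reproduce. I assume that nearly all participants are men or women.

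**Reading A: a person counts in every group they belong to.** Men + women = 30 and all four groups are equal, so each group has 30/2 = 15. That is 4 × 15 = 60 memberships over 30 people, or 2 each on average. The number who are both from an ethnic minority and use recreational drugs can be anything from 0 to 15, so the target is arithmetically attainable.

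**Reading B: four separate quotas.** Each has 30/4 = 7.5, so 7 to 8. People in the last two quotas are also men or women, so total men can range from 7.5 to 30 − 7.5 = 22.5.

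**Which reading fits the sentence?** Reading A delivers the balance of men and women that the sentence asks for. Reading B permits a split as uneven as 22.5 to 7.5, a ratio of 3 to 1, and so can fail the sentence it interprets. It also needs a rule for placing, say, a man from an ethnic minority who uses drugs, and the protocol has none. Reading A needs no such rule. The pairing of men and women in Section 7.2.2 is ordinary phrasing and favours neither.

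**If recruitment stops earlier.** At an assumed N of 20 the two readings give 20/2 = 10 and 20/4 = 5. The ratio stays at two and the argument for A is unchanged.

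**What could be lost in content.** The documents do not say how common any need is, so the prevalence p within a group is assumed. The chance that no one in k interviews from that group voices the need is (1 − p)^k:

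| p (assumed) | k = 8 | k = 15 |
|---|---|---|
| 0.10 | 0.43 | 0.21 |
| 0.20 | 0.17 | 0.04 |
| 0.30 | 0.06 | < 0.01 |

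These figures treat interviews as independent random draws and k as fixed. Sampling here is purposive and partly by chain referral, and the stop is adaptive. They also measure detection within a single group, an aim the protocol does not state: Section 5 plans one thematic analysis of all transcripts with no comparison by group. A need shared across the whole sample by 10% would be missed in 30 interviews with probability 0.9^30 = 0.04 under either reading. The table is an illustration and carries little weight.

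**What the study already records.** The pre-interview questionnaire in Section 5 collects gender, ethnicity and current drug use, so the mix can be tabulated at any time and set against either 15 or 7–8. One study coordinator handles screening (Section 7.3.1) and one person conducts the interviews (Section 5), which makes divergent targets within the study unlikely.

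**Timing.** The protocol version is dated 24 April 2017. Table 1 shows recruitment from November 2016 to July 2017, which is 9 months; November to April is 6 of them, leaving 3. Section 8.9 requires sponsor, ethics committee and R&D approval before any amendment is used.

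**The case for a change.** The best case for a change is that the mix is central to this study. The rationale says that the perspectives of these groups are usually left out of psychological pain treatment, and the sampling is offered as the remedy. No passage rules out the lower reading, eight participants who use recreational drugs would meet one reading and be about half of the other, and one sentence would settle it. The stop decision and the final report still lay ahead when this version was issued.

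Part of that stands. There is no counting rule, and the relation between mix and saturation is not spelled out. But this is missing detail that the sentence largely fills by itself, not a conflict between instructions. Purposive sampling, the several recruitment routes and the saturation stop can all be followed together. With no analysis by group planned, saturation is most naturally judged over the whole set of interviews.

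The one substantive change, declaring saturation only once the mix is reached, would act as a minimum composition. It could prolong recruitment of a hard-to-reach group after new interviews had ceased to add themes. A team could reasonably choose it, but leaving it out of a deliberately flexible qualitative design is equally reasonable.

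**Conclusion.** No change to the plan follows. The gap is real but small, and the team can fill it sensibly. The wording favours counting each participant in every group they belong to, which means about 15 of 30 in each; the alternative of 7 to 8 does not secure the balance of men and women that the same sentence requests. This rests on nearly all participants being men or women.

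Followed as written, the protocol still yields a sound pooled thematic analysis, and no estimate, test or error rate depends on the reading. The data needed to describe the achieved mix are already collected, and the signature page commits the chief investigator to explaining departures from the plan. A shortfall in any group can therefore be reported as a limit on the representativeness statements in the Background and Rationale and in Section 7.2.2. Whether the mix should also condition the saturation stop is a judgement for the study team.

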7.2.2 Sampling technique

Men and women, ethnic minorities, and people who use recreational drugs will be purposively sampled through HIV and pain clinics and community organizations and through chain referral sampling. Purposive sampling across participants with the range of demographic backgrounds identified will ensure that the interview responses are reflective of people with painful HIV-SN who might ultimately be referred to and receive the psychologically-based pain management treatment being developed.

7.3 Recruitment

7.3.1 Sample identification

Participants will be recruited from St Stephens Centre at Chelsea and Westminster Hospital NHS Trust and associated HIV and chronic pain clinics in London (e.g., Kobler Day Care Unit, John Hunter Clinic, Dean Street Clinic, and the 10 Hammersmith Broadway Clinic). Consultants at these clinics will identify potentially eligible participants in the course of their routine clinical care and will ask patients for permission to give their name and contact information to the study coordinator ([name]). For patients who agree to this, the study coordinator will conduct eligibility screening either in person at the clinic or over the telephone. We will also post recruitment advertisements in the waiting areas of these clinics which will instruct interested patients to contact the study coordinator directly to discuss the study and conduct eligibility screening.

Patients with HIV and painful peripheral neuropathy that have participated in a previous study at Chelsea and Westminster Hospital (the HIV-POGO Study) who have explicitly consented to be re-contacted for future studies will also be contacted to ask to inform them of the current study. A member of the research team from the HIV-POGO study will provide [name] with the contact information of individuals who have previously consented to be contacted for future studies. [name] will then contact these individuals by letter and telephone to provide information about the study and conduct eligibility screening.

Recruitment advertisements will also be sent to local HIV community groups to post in their centres and on their websites and social media accounts. Advertisements posted with these groups will ask potentially eligible and interested people to contact the study coordinator for further information and screening. Recruitment advertisements will likewise be posted on social media accounts for the study (e.g., Twitter). Lastly, eligible participants will be asked to give recruitment flyers to other potentially eligible individuals from their social network. Chain referral sampling is often used in qualitative research to recruit minority and stigmatized groups that are difficult to access (55).

In the recruitment process, potential participants will be informed that they will receive a £20 voucher and travel expenses up to £15.

7.2.2 Consent

Following screening, the study coordinator will review the participant information sheet with eligible participants either in person or over the telephone to describe the nature and objectives of the study and possible risks. Potential participants will be given the opportunity to ask the researcher any questions at this time. Potential participants will be given up to 1 month to consider the information and to decide whether they want to participate or not. Eligible individuals will be mailed a copy of the information sheet along with two copies of the consent form, and the pre-interview

questionnaires. Participants will be asked to bring the completed consent form to their interview appointment. The right to refuse to participate without giving a reason will be respected. We will emphasize that participants are free to withdraw at any time without consequence.

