4.2 Outcome

The interview responses will be used to develop and tailor an internet-delivered version of ACT for people with painful HIV-SN. Once developed, the new treatment will be tested in a feasibility trial (another study). It is hoped that tailoring the online ACT treatment based on the qualitative interview responses will increase the acceptability of the treatment and will improve treatment adherence rates.

5 STUDY DESIGN and METHODS of DATA COLLECTION AND DATA ANALYSIS

Participants will complete semi-structured interviews. Prior to the in-depth interview, participants will complete a questionnaire package at home to bring to their interview appointment (20-30 minutes to complete). The questionnaire package will consist of demographic and medical history questions, and symptom and functioning questionnaires. Individual in-depth semi-structured interviews will be conducted given the potentially sensitive nature of the questions and to maintain participants' anonymity. Participants will be given the choice to complete the interviews at the Imperial College London campus of Chelsea & Westminster Hospital or Guy's Hospital Campus of King's College London, according to their preference.

At the beginning of the interview appointment, the interviewer will conduct a 5 minute clinical examination to assess of symptoms and signs related to peripheral neuropathy. In the event that questionnaires are not completed prior to the interview session, participants will be asked to complete the questions at the interview appointment or at home and to mail them back in within 2 weeks. Participants who have not completed the questionnaires 3 weeks after the interview will receive a telephone reminder.

Pre-Interview Questionnaires

Demographic, Medical History, and Internet Use Questions: Participants will be asked to report on the following demographic and medical history questions: age, gender, ethnicity, sexual orientation, education, employment status, living situation, date of HIV diagnosis, history of and current antiretroviral treatment, duration of foot pain, other chronic pain diagnoses, mental health diagnoses, current pain medications, current alcohol and drug use, and frequency of Internet use.

Pain intensity and interference: The Brief Pain Inventory (BPI) will be used to assess pain intensity and the interference of pain with daily functioning in seven domains: general activity, mood,

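### HIV-identifying papers are posted to eligible people with no stated choice of route or address and no postal safeguard

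*Combined protocol and SAP*

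**What the plan says.** Section 7.2.2 (Consent; the number is also used for the sampling technique) sets out what happens after screening. The coordinator goes through the information sheet with the person, face to face or by telephone, and the person has up to a month to decide. On delivery the text says "Eligible individuals will be mailed a copy of the information sheet along with two copies of the consent form", and the pre-interview questionnaires go in the same mailing. No other route is mentioned.

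Section 5 describes the default use of the pack: "participants will complete a questionnaire package at home to bring to their interview appointment". If that has not happened, "participants will be asked to complete the questions at the interview appointment or at home and to mail them back in within 2 weeks". The items requested include "living situation, date of HIV diagnosis, history of and current antiretroviral treatment", as well as sexual orientation, mental health diagnoses, and alcohol and drug use.

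Section 7.3.1 adds a second use of post. For patients from a previous study who agreed to re-contact, the coordinator "will then contact these individuals by letter and telephone to provide information about the study and conduct eligibility screening".

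The Background and Rationale (sections 1 and 2) states that "findings from the available qualitative literature suggest that social stigma and interpersonal distrust may influence treatment engagement among individuals with HIV".

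**The concern.** A form that asks its recipient for the date of their HIV diagnosis tells anyone who sees it that the recipient probably has HIV. The plan sends that form to people's addresses and by default expects it to be filled in at home and brought to the appointment. For someone living with people who do not know their status, this is a route to disclosure created by the study, and it cannot be undone.

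There is also a sampling question. The study wants to learn how acceptable an internet-delivered treatment would be, and section 7.3.1 justifies chain referral by the need to reach stigmatized groups. People who worry about privacy at home hold views that bear on that aim. If some of them avoid a study that posts such papers, those views would be under-represented.

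**Working it through.** No formula applies, and the plan states no figure to reproduce. The check is a comparison of sections.

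1. **Route.** Section 7.2.2 (Consent) allows the information sheet to be reviewed in person or by telephone, but gives only mailing for delivery. Read literally, it covers a person screened at the clinic who could have been handed the pack.
2. **Content.** Section 5 lists the diagnosis date and antiretroviral history among the questionnaire items. These identify HIV before anything is written on the form. The alcohol and drug items do not: left blank, they say nothing about the recipient.
3. **Place of completion.** Section 5 makes home the default. Completion at the appointment is a fallback for forms not done beforehand, and by then the pack has already been posted.
4. **Knowledge of the household.** Section 5 asks about living situation, but inside the posted questionnaire. No earlier question about the home or about postal preference is stated.
5. **Safeguards.** Section 8.1 names interview distress and the handling of depression scores and other health risks. Section 8.7 covers study numbers, storage, transfer and access. Neither mentions outgoing or returned post. A study number protects the research record, not papers lying in the recipient's own home.
6. **The plan's own premises.** The background names stigma, section 5 chooses individual interviews partly for anonymity, and section 7.3.1 seeks stigmatized groups. The delivery rule does not follow through on these.

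**Size.** Section 7.2.1 plans about 30 participants. At one pack each, that is about 30 packs, plus one for each eligible person who is sent a pack and then declines. That last number is unknown and could be zero, because the order of posting and deciding is not stated.

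**Cost of completing forms on site.** Section 5 gives about 60 minutes for the interview, 5 for the examination and 20 to 30 for the questionnaires. The appointment would go from about 60 + 5 = 65 minutes to 65 + 20 = 85 or 65 + 30 = 95 minutes.

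**The case against.** The strongest reply is that nobody receives the pack without warning. Clinic patients give permission before their details are passed on, people answering advertisements make contact themselves, and previous-study patients agreed to be re-contacted. The coordinator then discusses the study and its possible risks and takes questions, so a person can object to posting or ask for another route. Nothing in section 7.2.2 forbids handing the pack over, and section 5 permits completion at the appointment. Patient representatives commented on the recruitment strategy, they and an HIV patient organization commented on the patient-facing documents, and ethics approval is required. The information sheet and consent form are not in the supplied text and may contain mailing arrangements.

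Much of this stands as mitigation. It does not close the gap: the protocol nowhere says that people are asked about posting, the fallback does not stop the mailing, and the accounts of patient input do not mention the delivery route.

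Three stronger readings are tempting and are not supported:

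- **That the pack carries HIV in its title.** The full study title names HIV but the short title does not, and the documents do not show which appears on the papers or on the section 7.3.1 letter. The point rests on the questionnaire items alone.
- **That posting discloses drug use.** Only a completed form could do that.
- **That posting deters the people most affected by stigma.** The background statement concerns engagement with treatment, not response to study post.

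**Conclusion.** The concern holds as a point about procedure and participant protection. The plan states a single delivery route for HIV-identifying papers, gives no choice of route or address, and lists no postal safeguard, so following it as written carries an avoidable risk of disclosing HIV status at home. It should be changed.

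The size is about 30 packs. A reader might go further and multiply 30 by an assumed share living with someone unaware of their status; 10 to 30% would give 3 to 9 people. The documents give no such share. The product would also count people in a certain household situation, not disclosures, since someone else must also see the papers. Deterrence is a possible selection effect, and its size cannot be estimated from the documents.

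Two assumptions remain: that some participants share a home with people who do not know their status, and that the documents not supplied contain no arrangement that already deals with this.

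**What to change.** In section 7.2.2 (Consent), replace the mailing sentence with a rule along these lines: at screening, the coordinator asks each person how and where they wish to receive the documents (handed over at the clinic or the appointment, or posted to an address they choose); nothing that identifies HIV is posted without that agreement; consent forms and questionnaires may be completed at the appointment. Keep the existing time to consider the information.

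In section 5, make completion at the appointment an equal option, not only a fallback. In section 7.3.1, use the short title on the letter to previous-study patients and on anything visible from outside. The letter also needs care in naming the previous study, whose own name begins with HIV. In section 8.1, list disclosure through post as a risk. The same handling can cover questionnaires mailed back and the results newsletter in section 9.1.

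The cost is one question in a conversation that already takes place, a few sentences of text, and 20 to 30 more minutes at the appointments where forms are completed on site. No research aim is affected.
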